5.4.4. Lost to Follow-up

When the Investigator has no news of the participant, the Investigator must make every effort to contact the participant or a person around the participant (phone calls, letters including registered ones, etc.) to establish the reason for the discontinuation of IMP and to suggest that the participant attends a withdrawal visit. If after the Investigator has completed all due diligence and all attempts to contact the participant fail, the Investigator can then declare the participant "lost to follow-up". The Investigator should document all contact attempts in the corresponding medical file.

6. TREATMENT OF PARTICIPANTS

IMP treatment of study subjects is outlined in the sections below. Complete details are provided in the pharmacy manual.

6.1. IMPs Administered

Product Description and Dosage Form	Concentration	Primary Packaging	Secondary Packaging
Ivosidenib / tablet	Tablets of 250 mg	One pillbox = 60 tablets of 250 mg	One box containing one pillbox of 60 tablets
Nivolumab / solution for injection	CC1 mg/mL	One vial = CCI mL CC1 mg/mL	One box containing one vial
Ipilimumab / solution for injection	CC1 mg/mL	One vial = CCI mL vial at CC1 mg/mL	One box containing one vial

It is recommended that each dose should be taken with or without food. Subjects taking ivosidenib with food should be advised to avoid grapefruit or grapefruit products and avoid

consuming a high-fat meal (Please refer to examples of low-fat and high-fat meals in [Appendix 12](#)).

For treatment dose modifications due to toxicities, please refer to Section [8.12](#). All the IMP tracking is managed in RTSM in real time. The procedures to be followed by the Investigator or authorized person are detailed in the training video embedded in RSTM or user manual.

6.2. IMP Dispensing

After completion of IRT, IMPs will be allocated, dispensed, and tracked via RTSM by the pharmacist/responsible individual of the healthcare establishment upon prescription of the Investigator only. The Investigator may only use the IMPs provided for the subjects involved in the study and treated under the Investigator's responsibility. All dosages of nivolumab and ipilimumab are prescribed to the subject and all dose changes during the study must be done via RTSM and recorded in the eCRF. For doses of ivosidenib, should a subject be unable to receive or return to the site for dose administration, delivery of the dose to the subject's home is permitted.

One drug kit of ivosidenib will be dispensed to the subject at Day 1 of each cycle. Nivolumab will be infused to the subject at Day 1 of each cycle. The number of vials of nivolumab allocated and the volume to infuse will be calculated in RTSM based on subject weight (from Cycle 1 to Cycle 4) and will be the same (48 mL) beginning at Cycle 5. At Day 1 of the first 4 cycles (Cycle 1 to Cycle 4), ipilimumab will be infused to the subject. The number of vials of ipilimumab allocated and the volume to infuse will be calculated based on subject weight.

The pharmacist/responsible individual of the healthcare establishment prepares the treatment in accordance with the Pharmacy Manual and documents it in the drug kit tracking file or equivalent validated tracking system. The individual then either sticks the drug kit label to the paper label collection form or assigns a drug kit number in the validated electronic tool based on site procedures, or scans the QR code in the validated electronic tool at the site level to log the dispensation.

The drug kit will be identified by a 6-digit number for identification, tracking, and stock management purposes.

6.3. Previous and Concomitant Treatments

6.3.1. Prior Medications and Procedures

All medications administered and procedures conducted within 4 weeks (28 days) prior to the first day of study drug administration (C1D1) are to be recorded in the eCRF.

As available, transfusion history, including red blood cell and platelet transfusion, for 56 days prior to C1D1 should be recorded at the Screening visit. This documentation should include dates of each transfusion and units administered.

6.3.2. Concomitant Medications and Procedures

All medications (other than IMPs) and significant non-drug therapies (including physical therapy, IV medications and fluids, herbal/natural medications, over-the-counter medications, and blood transfusions) administered during the study must be listed in the eCRF. If changes

occur during the study period, documentation of drug dosage, frequency, route, and date should also be included on the eCRF. The Investigator should instruct the subject not to take any additional medications (including over-the-counter products) during the study without prior consultation with the Investigator. In general, the use of any concomitant medication deemed necessary for the care of the subject is permitted in this study, except as specifically prohibited in Section 6.3.2.1. Information on prior anti-neoplastic treatment received for the primary diagnosis including prior radiation therapy will be collected.

A list of prohibited and unauthorized treatments by drug class can be consulted in the eCRF.

6.3.2.1. Prohibited Concomitant Therapies

The following concomitant therapies are prohibited for participants receiving treatment with ivosidenib in combination with nivolumab and ipilimumab.

- Strong inducers of CYP3A4 (Table 2, [Appendix 10](#)): Ivosidenib is mainly metabolized by CYP3A4; therefore, subjects should not use strong CYP3A4 inducers during treatment with ivosidenib.
- Sensitive CYP3A4 substrates with a narrow therapeutic window: Ivosidenib is an inducer of human CYP3A4/5; therefore, medications of sensitive CYP3A4 substrates with a narrow therapeutic window (Table 2, [Appendix 10](#)) should be avoided unless the subject can be transferred to other medications prior to enrolling.
- Immunosuppressive agents.
- Immunosuppressive doses of systemic corticosteroids. Participants are permitted the use of topical, ocular, intra-articular, intranasal, and inhalational corticosteroids (with minimal systemic absorption). Adrenal replacement steroid doses > 10 mg daily prednisone are permitted. A brief (less than 3 weeks) course of corticosteroids for prophylaxis (e.g., contrast dye allergy) or for treatment of non-autoimmune conditions (e.g., delayed-type hypersensitivity reaction caused by a contact allergen) is permitted.
- Any live/attenuated vaccine (e.g., varicella, zoster, yellow fever, rotavirus, oral polio and measles, mumps, rubella) during treatment and until 100 days post last dose.
- Any COVID-19 vaccine that cannot be rescheduled within 14 days prior to first dose of study drug or cannot be rescheduled during the DLT period.
- Any complementary medications (e.g., herbal supplements or traditional Chinese medicines) intended to treat the disease under study. Such medications are permitted if they are used as supportive care.
- Any concurrent systemic anti-neoplastic therapy (i.e., chemotherapy, hormonal therapy, immunotherapy, or standard or investigational agents for treatment of CCA). If alternative therapy is required for treatment of the subject's disease, the subject should be discontinued from the study treatment.
- Any non-palliative radiation therapy. Localized radiation therapy administered with palliative intent is permitted for subjects who continue to receive ivosidenib following documented disease progression and must be documented on the CRF.

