4.1.4.2. DLT Definition

All toxicities will be graded using the National Cancer Institute Common Terminology Criteria for Adverse Events (NCI CTCAE) Version 5.0 based on the Investigator assessment. The DLT window of observation will be the first 42 days of dosing (*i.e.*, Cycles 1 and 2) of the Safety Lead-In phase. The occurrence of any of the following toxicities during the first 42 days of dosing (*i.e.*, through Cycle 2) will be considered a DLT if assessed as unrelated to disease progression, intercurrent illness, or concomitant medications and considered to be related to study treatment by the Investigator.

In order to be evaluable for DLT, a subject must have had a DLT during Cycle 1 or 2, or have received 75% or more of the planned doses of ivosidenib and 2 full doses of nivolumab and ipilimumab through Cycle 2 and have not experienced a DLT. The subject must also be considered by the Investigator and Sponsor to have sufficient safety data available to conclude that a DLT did not occur.

Any of the following will be considered as DLTs that may be applicable for immuno-oncology (IO) therapy and ivosidenib:

- Any Grade \geq 4 irAE.
- Any Grade 3 irAE (excluding colitis, pneumonitis, or carditis) that does not improve to Grade 2 within 7 days after onset of the event despite optimal medical management including systemic corticosteroids or does not improve to Grade \leq 1 or baseline within 14 days.
- Any Grade \geq 3 colitis.
- Any Grade 3 non-infectious pneumonitis irrespective of duration.
- Any Grade \geq 2 pneumonitis that does not resolve to Grade \leq 1 within 7 days of the initiation of maximal supportive care.
- Any Grade \geq 2 myocarditis.
- Any Grade \geq 2 neurological toxicity including Guillain-Barre syndrome, myasthenia gravis, encephalitis, and myelitis.
- AST or ALT $> 3 \times$ the upper limit of normal (ULN) with concurrent increase in total bilirubin $> 2 \times$ ULN without evidence of cholestasis or alternative explanations, *e.g.*, viral hepatitis, disease progression in the liver (Hy's law).
- Any Grade \geq 3 non-irAE, except for those listed below.
- Any death unless related to disease progression, intercurrent illness, concomitant medications, or extraneous causes.

The DLT definition excludes the following conditions:

- Grade 3 QTc prolongation resolving to Grade 1 within 7 days.
- Grade 3 fatigue lasting \leq 7 days.

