5.4. Participant Withdrawal

5.4.1. Withdrawal Criteria

Premature discontinuation of IMP does not mean that the subject prematurely stops the participation in the study.

Subjects discontinuing study treatment for reasons other than withdrawal of consent from overall study participation will be expected to continue in the study including Safety Follow-up visits and be contacted for survival follow-up. Information to be collected during the last visit for these subjects is given in Section 5.4.3.

The reasons for premature discontinuation of IMP are:

- AEs, according to the judgment of the Investigator, including no recovery in safety parameters.
- Disease progression as assessed by the Investigator/site radiologist according to RECIST v1.1 ([Appendix 12](#)). Clinically stable subjects may continue beyond confirmed disease progression if benefits are expected to outweigh risks in the opinion of the Investigator and in consultation with the Sponsor.
- Clinical disease progression manifested by symptomatic deterioration.
- Completion of a maximum of 24 months of nivolumab (note that subjects receiving combination may continue to receive ivosidenib monotherapy).
- Pregnancy (for reporting, see Section [8.10.2.3](#)).
- Major protocol deviation if it interferes with the study evaluations and/or if it jeopardizes subject's safety, e.g., any medical event requiring administration of an unauthorized concomitant treatment (see Section [6.3](#)).
- Withdrawal of consent (only for IMP discontinuation): Subjects will be asked if they are willing to continue the safety and disease/survival follow-up.
- Physician decision (for reasons that cannot be included in any of the criteria listed above, for example, availability of a better therapeutic alternative for the subject).
- Study terminated by Sponsor.

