8.7. Immune-Related Adverse Events

Immune-mediated AEs are AEs consistent with an immune-mediated mechanism or immune-mediated component for which non-inflammatory etiologies (*e.g.*, infection or tumor progression) have been ruled out. IMAEs can include events with an alternate etiology that were exacerbated by the induction of autoimmunity. Information supporting the assessment will be collected on the participant's case report form.

Every AE must be assessed by the Investigator with regard to whether it is considered immune mediated. For events which are potentially immune mediated, additional information will be collected on the participant's case report form.

AEs associated with nivolumab and ipilimumab exposure may represent an immunologic etiology. These irAEs may occur shortly after the first dose or several months after the last dose of nivolumab and/or ipilimumab treatment and may affect more than one body system simultaneously. Therefore, early recognition and initiation of treatment is critical to reduce complications. Based on existing clinical study data, most irAEs were reversible and could be managed with interruptions of nivolumab and/or ipilimumab, administration of corticosteroids and/or other supportive care. For suspected irAEs, ensure adequate evaluation to confirm etiology or exclude other causes. Additional procedures or tests such as bronchoscopy, endoscopy, skin biopsy may be included as part of the evaluation. Based on the severity of irAEs, withhold or permanently discontinue nivolumab and/or ipilimumab and administer corticosteroids. Dose modification and toxicity management guidelines for irAEs associated with nivolumab and/or ipilimumab are provided in [Appendix 8](#) and [Appendix 10](#).

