8.12.2. Dose Modifications and Management Associated with Nivolumab and/or Ipilimumab

Dose delay criteria apply for all drug-related adverse events (regardless of whether the event is attributed to nivolumab or ipilimumab or both). Delay administration of both nivolumab and ipilimumab if any of the delay criteria are met. Delay nivolumab and ipilimumab dosing for any adverse event, laboratory abnormality, or intercurrent illness which, in the judgment of the Investigator, warrants delaying the dose of study medication.

For subjects who require the delay of nivolumab and ipilimumab, re-evaluate weekly, or more frequently, if clinically indicated and resume dosing when criteria to resume treatment are met. Continue tumor assessments per protocol even if dosing is delayed.

If discontinuation criteria are met for ipilimumab but not for nivolumab, treatment with nivolumab may continue; if nivolumab is discontinued, however, ipilimumab will not continue as monotherapy.

If a subject meets criteria for discontinuation of nivolumab/ipilimumab and Investigator is unable to determine whether the event is related to both or one study drug, the participant must discontinue both nivolumab and ipilimumab. Subjects may continue receiving ivosidenib. If subject permanently discontinues treatment from all three drugs, EOT and Safety Follow-up Visits will be completed, as well as PFS follow-up (if disease has not progressed) and survival follow-up visits.

Subjects may resume treatment with nivolumab/ipilimumab if they have completed AE management (*i.e.* corticosteroid taper) or are on ≤ 10 mg prednisone or equivalent, and meet the requirements per [Appendix 8](#) and [Appendix 9](#).

Prior to re-initiating treatment in a participant with a dosing delay lasting > 8 weeks for Q3 week treatment and 10 weeks for Q4 week treatment, the Medical Monitor (or designee) must be consulted.

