Appendix 9: Management Algorithms for Studies Under CTCAE Version 5.0

These general guidelines constitute guidance to the Investigator and may be supplemented by discussions with the Medical Monitor representing the Sponsor. The guidance applies to all immuno-oncology (IO) agents and regimens.

A general principle is that differential diagnoses should be diligently evaluated according to standard medical practice. Non-inflammatory etiologies should be considered and appropriately treated.

[figure not shown]
Corticosteroids are a primary therapy for IO drug-related AEs. The oral equivalent of the recommended IV doses may be considered for ambulatory subjects with low-grade toxicity. The lower bioavailability of oral corticosteroids should be taken into account when switching to the equivalent dose of oral corticosteroids.

Consultation with a medical or surgical specialist, especially prior to an invasive diagnostic or procedure, is recommended.

The frequency and severity of the related adverse events covered by these algorithms will depend on the IO agent or regimen being used.

GI Adverse Event Management Algorithm

Rule out non-inflammatory causes. If non-inflammatory cause is identified, treat accordingly and continue I-O therapy. Opiates/narcotics may mask symptoms of perforation. Infliximab should not be used in cases of perforation or sepsis.

[figure not shown]

Patients on IV steroids may be switched to an equivalent dose of oral corticosteroids (eg, prednisone) at start of tapering or earlier, after sustained clinical improvement is observed. Lower bioavailability of oral corticosteroids should be taken into account when switching to the equivalent dose of oral corticosteroids.

* Discontinue for Grade 4 diarrhea or colitis. For Grade 3 diarrhea or colitis, 1) Nivolumab monotherapy: Nivolumab can be delayed. 2) Nivolumab+ Ipilimumab combination: Ipilimumab should be discontinued while nivolumab can be delayed. Nivolumab monotherapy can be resumed when symptoms improve to Grade 1. Please refer to protocol for dose delay and discontinue criteria for other combinations.

Renal Adverse Event Management Algorithm

Rule out non-inflammatory causes. If non-inflammatory cause, treat accordingly and continue I-O therapy.

[figure not shown]

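### Protocol 6.3.2.1 prohibits immunosuppressive treatment with no exception for immune-related AEs, although the protocol's own toxicity guidance and DLT definition direct or presuppose systemic corticosteroids

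*Protocol*

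**What the plan says.** Protocol 6.3.2.1 prohibits two relevant classes for participants on ivosidenib with nivolumab and ipilimumab. The first is "Immunosuppressive agents", with no qualification. The second is "Immunosuppressive doses of systemic corticosteroids. Participants are permitted the use of topical, ocular, intra-articular, intranasal, and inhalational corticosteroids". The steroid bullet has three exceptions: routes with little systemic absorption, adrenal replacement, and a course under 3 weeks for prophylaxis or for a condition that is not autoimmune. The preceding section, 6.3.2, allows whatever medication care requires, but only where 6.3.2.1 does not prohibit it.

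Other sections point the other way:

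- Section 8.7 tells investigators, according to irAE severity, to "withhold or permanently discontinue nivolumab and/or ipilimumab and administer corticosteroids".
- Section 8.12.2 allows the antibodies to restart once participants have completed AE management (the example given is a "corticosteroid taper) or are on ≤ 10 mg prednisone or equivalent") and meet the requirements of Appendices 8 and 9.
- The DLT definition in 4.1.4.2 counts certain Grade 3 irAEs that fail to improve within 7 days "despite optimal medical management including systemic corticosteroids".
- Appendix 9 states: "Corticosteroids are a primary therapy for IO drug-related AEs". Its gastrointestinal section adds: "Infliximab should not be used in cases of perforation or sepsis". Its myocarditis section considers prophylactic antibiotics when immunosuppression is ongoing.

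Section 5.4.1 includes among the reasons for stopping IMP a major deviation that interferes with evaluations and/or endangers the participant. Its example, which cites Section 6.3, is "any medical event requiring administration of an unauthorized concomitant treatment".

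**The concern.** A site cannot satisfy 6.3.2.1 and Appendix 9 together as they are written. If it follows the prohibition, it does not give what Appendix 9 calls a primary therapy. If it follows Appendix 9, it gives something on the prohibited list. Section 14.2 closes the usual way out, because it permits no deviations and tells investigators not to ask for approval of one. Section 8.7 adds to the confusion: it sends readers to Appendices 8 and 10 for irAE management, but Appendix 10 contains the prohibited-medication tables and the algorithms are in Appendix 9.

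The stake is first patient safety. It is then reporting: whether a steroid-treated irAE appears as an important protocol deviation, and what reason is recorded if IMP stops, could depend on which section the reader applied. SAP 5.1.2 lists important deviations and SAP 5.1.1 presents reasons for treatment discontinuation. Neither says how irAE treatment is to be classified. Both bear on how the lead-in's safety and tolerability objective is read.

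**Working it through.** This is a check of text against text. The plan states no figure for it.

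**Step 1: does any exception in 6.3.2.1 reach irAE treatment?**

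- Low-absorption routes: no, because the treatment at issue is systemic.
- Adrenal replacement: no, this covers replacement dosing only.
- Short course for prophylaxis or non-autoimmune conditions: irAEs are not named. Section 8.7 describes these events as immune-mediated and refers to autoimmunity, so the wording points away from them.
- Immunosuppressive agents: no exception is stated.

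None of the three steroid exceptions covers an irAE, and the other bullet has none. No irAE exception appears elsewhere in the protocol or SAP.

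**Step 2: which sections direct or presuppose the prohibited treatment?**

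| Section | Systemic corticosteroids | Other immunosuppression |
|---|---|---|
| 4.1.4.2 | presupposed | not named |
| 8.7 | directed | not named |
| 8.12.2 | presupposed | not named |
| Appendix 9 | primary therapy | infliximab restricted in two settings, which implies use in others; ongoing immunosuppression foreseen |

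All four involve corticosteroids. Only Appendix 9 goes further, and its algorithm figures are not available in the text reviewed.

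**Step 3: what follows under 5.4.1?** Its example of a qualifying deviation points to Section 6.3, so literally prohibited irAE treatment could qualify. The reason is conditional on interference or jeopardy. Section 8.12.2 expressly lets dosing resume after a taper. Appendix 8 makes oral steroids a reason for permanent discontinuation for uveitis in particular, which would be unnecessary if steroid treatment of any irAE already had that effect. The sections do not agree on the consequence.

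**Step 4: how likely was the conflict to arise?** Protocol 2.5 reports, for 39 participants with biliary cancer on ipilimumab 1 mg/kg plus nivolumab 3 mg/kg, irAEs in 19 and Grade 3-4 irAEs in 6.

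- The protocol's percentages reproduce: 19/39 = 0.487 (49%) and 6/39 = 0.154 (15%).
- SAP Section 5 gives 7 enrolled. Assuming the same rates, the expected number with any irAE is 7 × 0.487 = 3.4, and with a Grade 3-4 irAE 7 × 0.154 = 1.1.
- Chance of at least one Grade 3-4 irAE: 1 − (33/39)^7 = 1 − 0.311 = 0.69.

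These are irAE frequencies over that study's follow-up, with nivolumab continued for up to 96 weeks on a different maintenance schedule. Rash or pruritus accounts for 33% of participants, and Section 2.5 does not say how many needed systemic steroids. The figures are therefore neither rates of steroid use nor rates for the 42-day DLT window.

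**Step 5: reporting.** If all 7 were dosed, classifying one participant differently moves a tabulated percentage by 1/7 = 14 points.

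**The case against.** The strongest defence is one of scope. The prohibited list applies to participants receiving the three-drug combination. Section 8.12.3 holds both antibodies for an immune-related event, 4.1.4.3 interrupts all three drugs for a DLT, and 8.12.2 asks for completed management or a low steroid dose before the antibodies return. On that reading the ban covers only periods of full combination dosing and the sections are compatible. The reading is coherent, but the protocol does not state it. Section 8.12.2 lets ivosidenib continue after the antibodies stop, and 6.3.2.1 itself contains provisions aimed at participants on ivosidenib, so the list does not plainly lapse when the antibodies are held.

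A second defence is that the instructions to use steroids are specific and repeated, so investigators would follow them. That is probably right, and it makes withheld treatment a possibility rather than an expectation. It does not settle how the treatment given is classified.

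Third, 6.3.2 mentions a list of prohibited and unauthorized treatments held in the eCRF, which is not in the documents. How it classes steroids for irAEs is unknown. This stands, and it limits the 5.4.1 link to something that could apply.

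A reader might also infer that steroid treatment of an irAE automatically ends study treatment. Section 5.4.1 does not say so, because its reason is conditional, and 8.12.2 provides for resumption. Nor do the documents show that the conflict inflates the DLT count: the 7-day criterion itself names systemic corticosteroids as part of the management it presupposes.

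**Conclusion.** The contradiction holds. A stated rule, followed literally, either forbids the protocol's own primary treatment for irAEs or makes giving it a breach, and no passage resolves this. For corticosteroids it rests on four locations. For other immunosuppressants it rests on Appendix 9 alone.

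Its size is qualitative. No response estimate, sample size or test is affected. With the rates in Protocol 2.5 as an assumption, at least one Grade 3-4 irAE among 7 participants had a probability of about 0.69, so the situation was more likely than not to arise. What remains exposed is the classification of deviations and discontinuation reasons in a very small set. A projection to the planned expansion cohorts might seem natural, but the SAP records that enrolment stopped at 7 and the study did not go on to expansion.

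The conclusion assumes that the figures not shown and the eCRF list do not contain an exception that the text lacks.

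**What to change.** The sponsor should reconcile 6.3.2.1 and 5.4.1 with 4.1.4.2, 8.7, 8.12.2 and Appendices 8 and 9:

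- In both bullets of 6.3.2.1, state how treatment given under Appendices 8 and 9 for a study-drug AE is classified.
- In 5.4.1, state whether such treatment counts as unauthorized concomitant treatment.
- In 8.7, check the reference to Appendix 10 against the location of the algorithms.
- Under SAP 5.1.2 and 5.1.1, apply the same classification to every participant, in the important-deviation listing and in the discontinuation reasons.

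Which clinical rule is right is for the sponsor to decide; none is proposed here.

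The cost is a few clauses in the protocol and a line in the deviation and disposition specifications. No new data or procedures are needed. With enrolment closed, the SAP lines can still be applied to the participants already treated, by case review.
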